Economic Measures

Inpatient costs will be measured through the collection of hospital billing and resource utilization information. In addition to index hospitalization costs, costs associated with subsequent readmissions will also be included in the study. Patients will also be asked at each follow-up visit if they have been hospitalized at another hospital and if yes for how long.

For those institutions who participate in Vizient (formerly the University Healthsystems Consortium [UHC]), hospital costs and resource utilization data will be collected. Vizient works with academic medical centers around the country to collect and warehouse clinical, safety, operational and financial data. These data are used to compare performance among peer hospitals and identify best practice patterns. Participating centers will provide unique trial information and the dates of participation in the trial to Vizient who will provide a de-identified data set of the financial data for the trial to the investigators for analysis.

For institutions who do not participate in Vizient, hospital billing data from the UB-92 form will be collected in a de-identified manner from the institutional billing departments. As hospitalization practices differ substantially and detailed accounting data are unavailable for the participating Canadian and German centers, the cost and cost-effectiveness analysis will be restricted to US centers only.

Safety

Adverse Events

Please refer to the CTSN Clinical and Adverse Event Reporting and Adjudication Procedures guidance document for general reporting procedures and guidance on the determination of intervention-expected AEs.

Specific Adverse Event Definitions

AV Conduction Block leading to Permanent Pacemaker Placement

See “Cardiac Arrhythmias” below

New-onset Post-Operative Atrial Fibrillation

See “Cardiac Arrhythmias” below

Bleeding

A bleeding event is defined by any one of the following:

- Transfusion of > 5 units RBC within the first 24 hours following surgery
- Death due to hemorrhage
- Re-operation for hemorrhage or tamponade

NOTE: Hemorrhagic stroke is considered a neurological event and not as a separate bleeding event.

Cardiac Arrhythmias

Any documented arrhythmia that *results in clinical compromise* (e.g., hemodynamic compromise, oliguria, pre-syncope or syncope) that requires hospitalization or requires a physician visit or occurs during a hospital stay.

Cardiac arrhythmias are classified as follows:

- Cardiac arrest

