For computing sample size, we assume that at two years post randomization, 25% of patients treated with only MVS will experience the primary composite endpoint. We believe a meaningful effect worth detecting is at least a 50% relative reduction to 12%, for patients undergoing TV annuloplasty in addition to MVS. A total of 400 patients, randomized with equal probability to each arm, provides approximately 90% power to detect such a difference. For simplicity, power is based on a 0.05 level two-tailed chi-squared test. The sample size takes account of a potential single interim analysis to be performed in addition to the final analysis, and a minimal (less than 3%) rate of crossover.

Randomization Design and Procedure

Patients will be randomized using a 1:1 allocation to TV annuloplasty plus MVS or to MVS alone. The randomization will be stratified by clinical center (i.e., a separate randomization scheme will be employed in each center) and by whether severity of TR is moderate or not. A random permuted block design will be employed, with blocks of size 2, 4, or 6 randomly chosen. Randomization will be implemented as described in Randomization Section.

Data Monitoring and Analysis

Methods of Analysis

The primary outcome of this trial is treatment failure defined as the composite of (1) death from any cause, (2) reoperation for TR, (3) presence of severe TR at two years post randomization or, for patients enrolled with less than moderate TR and annular dilatation, progression by two grades (i.e., from none/trace TR to moderate TR) at two years. The null hypothesis is that there is no difference in the probability of treatment failures at two years post randomization between patients randomized to undergo TV repair during MVS

compared to patients randomized to undergo MVS alone. The primary null hypothesis will be tested in an intent-to-treat analysis using a 0.05 level two-tailed normal approximation (Wald) test.

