A log binomial regression model will be used to estimate and test differences in treatment failure between randomization groups. Similar to the logistic regression model, the log-binomial model is a generalized linear model. The models differ only in the link function used for the "success" probability p ; logit (log odds) for logistic regression and log (log p) for log-binomial. The different links parameterize the model differently, with parameters of the log-binomial model yielding log relative risks rather than the log odds ratios of the logistic model.

The basic form of the log binomial models is:

$$\log P[Y_i = 1 | X_{1i}, X_{2i}] = \beta_0 + \beta_1 X_{1i} + \beta_2 X_{2i},$$

where Y_i is a binary indicator of treatment failure for the i^{th} patient, X_{1i} is a binary indicator of randomization assignment for the i^{th} patient and X_{2i} is an indicator of moderate or less TR at baseline, a factor by which randomization will be stratified. While randomization will also be stratified by randomizing center, the analysis will not adjust for center due to their relatively large number compared to the proposed sample size. The exponentiated estimate of β_1 (e^{β_1}) in this model is the risk ratio for the composite endpoint for patients randomized to TV repair compared to patients randomized to no TV repair. The risk ratio and its associated 95% confidence interval will be used to quantify the relative risk of the composite endpoint. Differences between randomization groups in the risk of the composite endpoint will be determined by testing the null hypothesis $H_0: \beta_1 = 0$ versus a two-sided alternative ($H_1: \beta_1 \neq 0$) using a 0.05 level intention-to-treat normal approximation test (i.e., the Wald test).

Imputation of missing data

We expect relatively few patients to be missing the primary endpoint due to withdrawal or refusal. Patients with missing data will have their 24 month status imputed via multiple imputation assuming that the data are missing at random, i.e., the missing nature of the variable is independent of the value of the variable given the observed data. The specific imputation model to be used will be determined prior to examination of any outcome data and will be included in an accompanying statistical analysis plan.

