The main feature of the imputation approach is the creation of a set of clinically reasonable imputations for treatment failure for each patient with missing data. This will be accomplished using a set of repeated imputations created by predictive models based on the majority of participants with complete data. The imputation models will reflect uncertainty in the modeling process and inherent variability in patient outcomes, as reflected in the complete data.

After the imputations are completed, all of the data (complete and imputed) will be combined and the analysis performed for each imputed-and-completed dataset. Rubin's method of multiple (i.e., repeated) imputation will be used to estimate treatment effect. We propose to use 30 datasets. For simplicity our primary analysis will not be stratified by clinical center, although the randomization will stratify by clinical center. This should result in only a small loss of efficiency.

Interim Analysis

We plan to perform a single interim analysis with respect to the primary endpoint to give the option of stopping early should results strongly favor one arm or the other. The proposed timing of this analysis is at 0.5 on the information scale, i.e., after one-half of patients (200) reach the primary endpoint. The utility of performing this analysis will depend on the rate of accrual of patients into the trial. As the decision to terminate early would likely occur after most, if not all, patients were randomized, the principal benefit of early termination would be prompt dissemination of results, and no further randomization to an inferior treatment. A group sequential procedure will be used to allow for flexibility in the number and timing of interim analyses should the DSMB choose to modify the proposed plan, or should accrual mitigate the usefulness of an interim look. We will use the Lan-DeMets approach, implementing an O'Brien-Fleming-type spending function that allots most of the type I error to the final look. The resulting critical values to be used for each analysis are 2.963 at the first interim analysis, 1.969 at the final analysis.

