Hospital length of stay and days in Intensive Care: We will compare hospital LOS and days spent in ICU between treatment groups, separately by region (North America and Germany). A Wilcoxon Rank-Sum test will be used to test for differences within each geographic subgroup.

Hospital readmission: Rates of all-cause hospitalizations and rates of cardiovascular and heart failure specific hospitalizations, both within 30 days and within two years will be compared using Poisson regression.

Costs and Cost-Effectiveness

Cost

Cost will be calculated by converting charges to cost using institution specific Ratio-of-Cost-to-Charges (RCCs). Institution-specific cost reports will be used to calculate RCCs for each major resource category. Cost data will only be collected in the North American sites. Costing data will be compared by Student's t test after log transformation.

Independent predictors of cost, including baseline factors, operative factors and postoperative events, will be determined by multivariate regression analysis.

Cost-Effectiveness

The primary objective of the CEA is to estimate the incremental CE ratio (ICER) of the intervention under investigation as compared to the study-defined alternative. This ratio measures the ratio of the difference in costs and outcomes between the two study arms, with outcomes measured as quality-adjusted life-years (QALYs). QALYs reflect an individual's preference for both quantity and QOL in a single measure that facilitates comparisons across diverse treatment modalities. We will also compute net health benefits (NHB) as an alternative way of looking at cost-effectiveness. This parameter compares the incremental effectiveness of an intervention with the minimum health effect

that society would demand in return for the investment; i.e., with the health produced by investing at the societal ceiling cost-effectiveness ratio (CR).

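### Log cost is compared by a t test that ignores clinical center although randomization is blocked within center; if cost varies between centers, the test is conservative and loses power

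*Protocol*

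**What the plan says.** Protocol, Randomization Design and Procedure: "The randomization will be stratified by clinical center (i.e., a separate randomization scheme will be employed in each center"), and also by whether TR is moderate. On the blocks: "A random permuted block design will be employed, with blocks of size 2, 4, or 6 randomly chosen".

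Protocol, Costs and Cost-Effectiveness, repeated in SAP 6.5.2.7: charges are converted to cost with each institution's own ratio, and then "Costing data will be compared by Student's t test after log transformation". A separate multivariate regression looks for predictors of cost. It is not the arm comparison, and center is not among the factors listed.

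Center is discussed only for the primary endpoint. Under Methods of Analysis (and SAP 6.5.1.2), "the analysis will not adjust for center due to their relatively large number compared to the proposed sample size". Under Imputation of missing data, the protocol says of the unstratified primary analysis: "This should result in only a small loss of efficiency". Nothing comparable is said about cost.

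For length of stay and ICU days, compared separately in North America and Germany: "A Wilcoxon Rank-Sum test will be used to test for differences within each geographic subgroup".

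**The concern.** When patients are blocked within center, the two arms have nearly the same mix of centers, so an expensive hospital raises the mean of both arms alike and mostly drops out of the difference. The two-sample t test does not use this. It treats all variation within an arm as noise, including variation between hospitals. Its standard error is then larger than the real sampling error, a nominal 5% test rejects less often than 5% under the null, and power is given away.

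The plan's reasons for omitting center do not carry over. A log-binomial model with many center terms and few failures per center is hard to fit. A linear model for a continuous outcome with a single variance component for center is not. At stake is the chance of detecting a real cost difference from adding annuloplasty. The primary result is not touched.

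**Working it through.** **The plan's own figure.** There is none for cost: the documents state no US sample size, standard deviation, ICC or power for it. The 90% power statement concerns the primary endpoint and does not bear on this point.

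**Inputs from the documents.** 1:1 allocation; blocks of 2, 4 or 6 within center and TR stratum; two-sided 0.05 (SAP 6.1); up to 50 centers overall.

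**Assumed inputs.** ICC ρ from 0 to 0.4; 200 patients in 25 centers of unequal size.

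**Formula.** Set the total variance of log cost to 1.
- Standard error the t test reports: about √(4/N).
- True standard error if the arms are exactly balanced within centers: √(4(1−ρ)/N).
- Ratio of reported to true: 1/√(1−ρ). N cancels.
- True type I error: 2Φ(−1.960/√(1−ρ)).
- Power of the t test for an effect that gives 80% with center in the model: Φ(2.802 − 1.960/√(1−ρ)), where 2.802 = 1.960 + 0.842.

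At ρ = 0.2: √0.8 = 0.894 and 1.960/0.894 = 2.191. Type I error = 2Φ(−2.191) = 2.8%. Power = Φ(2.802 − 2.191) = Φ(0.610) = 72.9%.

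| ρ | reported/true SE | type I error | t-test power | loss from 80% |
|---|---|---|---|---|
| 0.05 | 1.03 | 4.4% | 78.5% | 1.5 |
| 0.1 | 1.05 | 3.9% | 76.9% | 3.1 |
| 0.2 | 1.12 | 2.8% | 72.9% | 7.1 |
| 0.3 | 1.20 | 1.9% | 67.7% | 12.3 |
| 0.4 | 1.29 | 1.1% | 60.7% | 19.3 |

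**Simulation with incomplete balance.** Small centers leave blocks unfinished, so the table is the limiting case. With 200 patients, 25 unequal centers, two TR strata and blocks of 2/4/6, at ρ = 0.1, 0.2, 0.3 and 0.4:
- type I error of the t test was 4.5%, 3.4%, 2.7% and 1.8%;
- its power was 79%, 74%, 70% and 65%, against 79–81% with center in the model. The loss is thus 0–2, 5–7, 9–11 and 14–16 points.

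**A second simulation** used 200 patients in 20 centers, with the effect sized for 80% t-test power. At ρ = 0.2 the t test reported a standard error of 0.140 against a true 0.131; at 0.3, 0.139 against 0.121. Adding center raised power from 81% to 87% and from 83% to 91%. With 280 patients in 30 centers the results were nearly identical.

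**Cost of the random intercept when it is not needed.** At ρ = 0, power with a random center intercept and with the t test differed by at most 0.3 points (79.2 and 79.1% for 200 patients in 25 centers; 78.2 and 78.5% for 100 in 20). The mixed model held type I error near 5%. In the same settings the t test was 5–7 points lower in power at ρ = 0.2 and 17–19 lower at 0.4.

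**Length of stay and ICU days.** The obvious stratified alternative is the van Elteren test (Wilcoxon stratified by center). With single-patient centers pooled, power was as follows:

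| ρ | 200 patients/25 centers: Wilcoxon, van Elteren | 100/20: Wilcoxon, van Elteren |
|---|---|---|
| 0 | 77%, 72% | 77%, 68% |
| 0.05 | 81%, 75% | 78%, 72% |
| 0.1 | 79%, 76% | 79%, 73% |
| 0.2 | 80%, 81% | 81%, 80% |

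It loses power at low ρ and only breaks even near 0.2.

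**The case against.** The strongest objection is that the documents do not show a center effect on cost within the US. A reader might infer one from the Economic Measures section, which says "As hospitalization practices differ substantially". But that sentence is about Canadian and German centers, and it leads to restricting the cost analysis to US centers; it is silent on variation among US hospitals. The institution-specific ratios do not prove a center effect either, since they should reduce differences in mark-up. This objection stands. The ICC is unknown, and at 0.1 or less the loss is small.

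A second objection is that adjusting for many centers costs degrees of freedom, which is the protocol's own reason for the primary endpoint. That has force against fixed center effects: in a small simulated subset (100 patients, 20 centers, no center effect) center-adjusted regression lost 5 points. It does not reach a random intercept, which cost essentially nothing.

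Third, the test is only conservative, the outcome is secondary, and no interval is planned for this comparison. The cost-effectiveness analysis has its own probability intervals. All true, and these facts limit the importance of the point. SAP 6.1 also allows another method if the planned one proves unsuitable, but that decision would be taken during data analysis rather than beforehand.

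A reader might also extend the point to length of stay and ICU days and call for van Elteren tests. The power figures do not support that, and those outcomes are already split by region.

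**Conclusion.** The omission is real, and no reason given in the documents covers it. Its consequence is conditional: if log cost varies between US centers, the planned t test is conservative and loses power. Under the assumed inputs the loss is about 0 to 3 points at an ICC of 0.1 or less, about 7 at 0.2 and about 12 at 0.3 (5–7 and 9–11 where balance within centers is incomplete), with type I error of about 3% at 0.2. These figures rest on a normal model for log cost and on an ICC, US sample size and number of US centers that the documents do not give.

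The documents do not support saying that cost is known to depend heavily on center, that power is certainly lost, that the estimate is biased, or that false positives rise. The point concerns secondary economic outcomes only. It is a free improvement, not a correction of an invalid test.

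**What to change.** In SAP 6.5.2.7, and in the matching Cost paragraph of the protocol, replace the t test on log cost with a linear mixed model for log cost containing arm and a random intercept for clinical center, and report the arm effect with its 95% confidence interval.

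Keep the planned Wilcoxon tests for length of stay and ICU days in SAP 6.5.2.6. At most, add a supportive model of those outcomes with a random center intercept.

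In the same edit, reconcile which centers supply cost data: Economic Measures restricts the analysis to US centers, while the Cost paragraph and SAP 6.5.2.7 refer to North American sites. This decides which centers enter the model.

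The cost is a few lines of text. Center is already recorded as a randomization stratum, no new data are needed, and the SAP allows revision before data lock. The change leaves the incremental cost-effectiveness ratio and its intervals as planned.

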Appendix I: Moderate Tricuspid Regurgitation Trial Echocardiographic Image Acquisition Protocol

General Considerations:

- For the echocardiogram, the patient will be positioned in left lateral recumbency or in the position that permits optimal imaging. All images should be acquired during quiet respiration unless otherwise specified.
- At least 3 and no more than 5 cardiac cycles are requested for two-dimensional imaging unless otherwise specified. At least 5 cardiac cycles are required for spectral pulsed wave (PW) and continuous wave (CW) Doppler. For patients in atrial fibrillation, a minimum of 2 captures of 5 consecutive cardiac cycles are required. Unless otherwise specified, depth should be adjusted to maximize the image while including all necessary structures. Harmonic imaging should be employed to optimize visualization of endocardial borders.
- All PW, CW Doppler and m-mode recordings will be performed at a sweep speed of 100 mm/sec. Gain should be adjusted to reduce excess noise. Color Doppler Nyquist limits will be adjusted to the range of 50-70 cm/sec, unless otherwise specified. The following protocol is required however additional images should be obtained at the discretion of the sonographer/physician.

I. Protocol for Transthoracic Echocardiogram (TTE) pre and post-surgery

1. Parasternal long axis
 - 2D image
 - Color Doppler across aortic and mitral valves
 - Zoom image of LVOT
 - Zoom image of vena contracta
2. Parasternal right ventricular inflow view of the tricuspid valve
 - 2D image include RV and RA (optimize endocardium)
 - Color Doppler across tricuspid valve (TV) including distal jet into RA
 - Zoom view of TV annulus (for measurement of TV annulus)
 - Zoom view of vena contracta proximal jet of TR
 - Zoom view of the proximal flow convergence region of the TR jet after baseline shifted downward (same direction as TR jet flow) to a Nyquist of 25-35 cm/s
 - Continuous wave Doppler across TV valve to estimate TV gradient.
3. Parasternal outflow view of the pulmonic valve
 - 2D
 - Color Doppler across PV

- Pulse wave Doppler
- CW of the pulmonary valve
- Zoom 2D image of pulmonary valve annulus for measurement of the pulmonary annular diameter.

4. Basal PSAX (at the aortic valve level)

- 2D image include TV, short axis of aortic valve and RVOT
- Color Doppler of TV include distal jet into right atrium
- Zoom view of Color Doppler view of vena contracta of TR
- Zoom view of the proximal flow convergence region of the TR jet after baseline shifted downward (same direction as TR jet flow) to a Nyquist of 25-35 cm/s
- Pulsed Doppler sample of pulmonary flow at the level of the pulmonary valve to measure pulmonary velocity time interval (VTI) opening and closing transients of the pulmonary valve should be recorded.

5. PSAX of ventricles: ensure on-axis views and include right ventricle

- Level of the mitral valve when both anterior and posterior leaflets are visualized.
- Mid-papillary muscle level.
- Level of the apex

6. Apical 4-chamber view

- Full sector to include all four chambers
- Focus on right heart: 2D to Include RV and RA, making sure to include lateral wall of RV (often requires a slight medial tilt of transducer)
- Zoom view of RV only (include base of RV/TV annulus and optimize RV endocardium)
- Color Doppler across TV one including right atrium to capture the distal jet taking care to include wall-impinging eccentric jets in the region of interest.
- Zoom view of TV annulus (for measurement of TV annulus)
- Zoom view of Color Doppler across TV to image the vena contracta of the TR jet
- Zoom view of the proximal flow convergence region of the TR jet after baseline shifted downward (same direction as TR jet flow) to a Nyquist of 25-35 cm/s
- PW of TV at leaflet tips and at level of TV annulus
- CW of TV for estimation of pulmonary artery systolic pressure
- M-mode across lateral tricuspid annulus (for TAPSE measurement)
- Tissue Doppler of lateral tricuspid annulus (to measure peak annular velocity)
- Focus on left heart:

- 2D include both LV and LA
- Zoom view of LV only (avoid foreshortening of LV apex)
- Color Doppler across MV one including left atrium to capture the distal jet taking care to include wall-impinging eccentric jets in the region of interest.
- Zoom view of MV annulus (for measurement of MV annulus)
- -Zoom view of the proximal flow convergence region of the MR jet after baseline shifted downward (same direction as MR jet flow) to a Nyquist of 30-40 cm/s
- PW of MV at leaflet tips and at level of MV annulus
- PW Doppler of right pulmonary vein flow. The sample volume should be placed at least 1 cm within the pulmonary vein
- CW of MV
- Tissue Doppler of lateral and septal mitral annulus

7. Apical 5-Chamber view

- Color flow Doppler across LVOT/Aortic valve
- PW Doppler in left ventricular outflow tract positioned such that closing artifact but not opening artifact of the valve is visible.
- CW Doppler through the LVOT/aortic valve.

8. Apical 2-chamber view

- 2D image include left ventricle and left atrium
- Zoom view to include LV only (avoid foreshortening of LV apex)
- Color Doppler cross mitral valve including distal jet into left atrium

9. Apical 3-chamber view (aka apical long-axis view)

- 2D image include left ventricle and left atrium
- Color Doppler cross mitral valve including distal jet into left atrium
- PW Doppler in left ventricular outflow tract
- CW Doppler through the LVOT/aortic valve.

10. Subcostal imaging

- 2D of Inferior vena cava with and without a “sniff” (5-10 beat loop).
- Pulse wave of hepatic vein flow
- Color Doppler of IVC and RA junction
- Color Doppler of inter-atrial septum to interrogate presence of SD.
- 4-chamber view showing RV, RA LA and LV
- Color Doppler of TV and MV in 4 chamber subcostal view

- SAX views (particularly if parasternal evaluation was limited).

11. Contrast will be used for endocardial border delineation when less than 80% of the endocardium can be visualized on the harmonic image.

Note: Addition of any non-standard imaging will be coordinated in collaboration with the selected Core Laboratory under a protocol amendment and should be obtained at the discretion of the sonographer/physician.

II. Protocol for Intra-operative Transesophageal Echocardiogram (TEE)

Intra-operative TEE imaging will be performed on all specified index operative procedures in the CTSN clinical trials, consistent with standard clinical care. For the purposes of the CTSN trials, the clinically indicated TEE's will be performed according to the standardized protocol below. The echos will be over-read by the echo core lab.

Valvular evaluation should always include Color Doppler and Pulsed/Continuous Wave Doppler as appropriate. A comprehensive intra-operative multiplane TEE as defined by the ASE/SCA Guidelines (Shanewise JS et al. J Am Soc Echocardiogr 1999; 12:884-900) should be performed.

Pre-Procedure Imaging

The following checklist may be used with appropriate Doppler performed for valvular assessment:

1. Mid and High esophageal views
 - 4 Ch view (of entire LV/RV); maximize endocardial definition.
 - Tricuspid Valve/Right Ventricle/right atrium/Interatrial Septum
 - 4 Chamber view angled to focus on right heart –both include RA and RV
 - Focus on TV including right atrium by changing depth to and obtain 2D image and color Doppler at 0, 60, 90 and 120-140 degrees; please include entire TV annulus
 - Interatrial septum (IAS) at (50 to 70 degrees-with aortic rim in view) and bicaval view (90-110°) 2D and Color Doppler across IAS
 - (if 3D available) 3D TEE image of TV and RV at 0 degrees and 60 degrees (Full volume acquisitions-1 beat and either 4 beat or HVR mode-please hold respiration for latter)
 - (if 3D available) 3D color Doppler TEE of TR jet at 0 and 90 degrees (Full volume acquisition-1 beat and either 4 beat or HVR mode-please hold respiration for latter)
 - 2. Mitral Valve: (lower depth to maximize visualization of the valve but include chordal attachments to the papillary muscle level). Please obtain 2D and color

Doppler images of the mitral valve and chordal structures. For color Doppler assessment: Please adjust color Doppler settings to optimize visualization of MR jet area and vena contracta (Nyquist between 50-70 cm/s). Please also obtain in at least one view: baseline shifting (in direction of MR jet flow) to Nyquist of 0.3 to 0.4 m/s) with Zoom mode on the proximal flow region. This is for PISA calculation.

Please obtain views of the mitral valve in the following planes:

- Transverse Plane (0°)
 - Change depth to image entire LV as well; maximize endocardial definition)
- Commissural View (60°)
 - Change depth to image entire LV as well; maximize endocardial definition.
- Two-chamber View (90°)
- Three-chamber View (120-140°)
- Record CW of MR in at least one plane
- Record PISA region after baseline shifting Nyquist upward (in direction of flow) to 40 cm/s. Please record 3-5 beats and not a single frame

3. LVOT/AV/Aorta

- Long-axis view (120-140°) 2D and with color Doppler
- Ascending aorta (mid to high esophageal view) (90° to 110)
- Ascending aorta SAX views (0°, high esophageal)
- AV SAX (30°, mid esophageal) with color Doppler

4. Main PA/PV

- Bifurcation view (0-30°, high esophageal)
- RVOT view (70°, mid esophageal)

5. Left atrial appendage

- 2D at 45, 75, and 120-135 degrees.

6. Pulmonary vein pulse wave Doppler: Sample volume placed in the vein, 1 cm from the orifice.

- One left and one right PV

7. Transgastric views

- Three 2D short axis views are requested
 - Mitral valve level
 - Mid papillary muscle
 - Apical level.
- Short axis images of the right ventricle and tricuspid valve (0 degrees)
 - Long axis of right ventricle and tricuspid valve (60-100 degrees)

- Pulse wave of hepatic vein flow
- Deep Gastric views
- 5Ch view Aortic valve (with color, PW and CW Doppler)

8. Aorta

- Thoracic aorta (short axis views)
- Aortic arch (SAX and LAX views)

Post-procedure Imaging

A full post-procedure TEE should be obtained if time permits. Otherwise, the study should be tailored to the procedure performed, including a minimum of the following:

1. Tricuspid Valve/right ventricle
 - Right heart –both include RA and RV at 0 and 60, 90 degree view
 - 2D and color Doppler (for jet area and vena contracta) at 0, 60, 90 and 120-140 degrees; please include entire TV annulus
 - Pulse and continuous wave across tricuspid valve
 - (If 3D TEE available)-3D TEE image of RA and RV at 0 degree (Full volume acquisitions-1 beat and either 4 beat or HVR mode-please hold respiration for latter)
 - (if 3D available)-3D TEE image of TV and RV at 0 degrees and 60 degrees (Full volume acquisitions-1 beat and either 4 beat or HVR mode-please hold respiration for latter)
 - (if 3D available)-3D color Doppler TEE of TR jet at 0 and 90 degrees (Full volume acquisition-1 beat and either 4 beat or HVR mode-please hold respiration for latter)
2. Mitral valve
 - 2D and color Doppler of mitral valve at 0, 60, 90, and 120 degrees
 - (include MR jet area and vena contracta for color Doppler views)
 - Zoom of PISA region (if MR is >mild by semi-qualitative assessment) with baseline shift to 40 cm/s
 - Continuous wave Doppler to assess post-procedure gradients and MR jet velocity
 - Pulmonary vein (one left and one right PV) pulse wave Doppler: Sample volume placed in the vein, 1 cm from the orifice.
3. Left ventricle
 - Mid-Esophageal views of LV at 0 and 60 degrees

III. Moderate TR: Echocardiographic Measurements

The degree of tricuspid valve regurgitation will be categorized according to American Society of Echocardiography guidelines as none/mild/moderate/severe (J Am Soc Echocardiogr 2003; 16:777-802).

Parameter	Mild	Moderate	Severe
Tricuspid valve	Usually normal	Normal or abnormal	Abnormal/Flail leaflet/Poor coaptation
RV/RA/IVC size	Normal*	Normal or dilated	Usually dilated**
Jet area-central jets (cm ²) [§]	< 5	5-10	> 10
VC width (cm) [¶]	Not defined	Not defined, but < 0.7	> 0.7
PISA radius (cm) [¶]	≤ 0.5	0.6-0.9	> 0.9
Jet density and contour-CW	Soft and parabolic	Dense, variable contour	Dense, triangular with early peaking
Hepatic vein flow†	Systolic dominance	Systolic blunting	Systolic reversal

CW, Continuous wave Doppler; IVC, inferior vena cava; RA, right atrium; RV, right ventricle; VC, vena contracta width.

* Unless there are other reasons for RA or RV dilation. Normal 2D measurements from the apical 4-chamber view: RV medio-lateral end-diastolic dimension ≤ 4.3 cm, RV end-diastolic area ≤ 35.5 cm², maximal RA medio-lateral and supero-inferior dimensions ≤ 4.6 cm and 4.9 cm respectively, maximal RA volume ≤ 33 ml/m²(35;89).

** Exception: acute TR.

§ At a Nyquist limit of 50-60 cm/s. Not valid in eccentric jets. Jet area is not recommended as the sole parameter of TR severity due to its dependence on hemodynamic and technical factors.

¶ At a Nyquist limit of 50-60 cm/s.

¶ Baseline shift with Nyquist limit of 28 cm/s.

† Other conditions may cause systolic blunting (eg. atrial fibrillation, elevated RA pressure).

A. Tricuspid Valve/Right atrium and right ventricle

The following variables will be measured:

1. Degree of tricuspid regurgitation categorized as:
 - a) None/Trace
 - b) Mild
 - c) Moderate
 - d) Severe
2. Jet area of TR
3. Vena contracta
4. EROA by PISA
5. TV annulus dimension (Apical 4 Chamber)
6. TV: Mechanism of TR: Primary vs secondary
7. RA volume (ml)
8. RV function categorized as:
 - a) Normal
 - b) Mildly impaired
 - c) Moderately impaired
 - d) Severely impaired
9. Tricuspid annular peak systolic excursion (TAPSE)
10. Peak tricuspid annular velocity (PTAV)

11. RV fractional area change (%)
12. RV size categorized as
 - a) Normal
 - b) Mildly dilated
 - c) Dilated
13. RV dimension (apical 4 chamber view)
